## **1.2 SAMPLE SIZE DETERMINATION**

The sample size is based on being able to claim superiority of alicaforsen over placebo; at Week 10 separately for each of the two co-primary endpoints.

The primary analysis will be based on a Cochran-Mantel-Haenszel Test (CMH) stratifying by region. In addition, a difference in the proportion of subjects with treatment success (and the associated estimated 95% confidence interval) will be presented based on the Z-test.

For both co-primary end-points, it is assumed in the sample size calculation that 50% of patients on alicaforsen and 20% on placebo will have a successful treatment outcome. Based on a 1:1 design, 63 subjects per treatment group will be required to show superiority (alicaforfen to placebo odds ratio >1) using a two-sided CMH Test at the 5% significance level and with 95% power. For the same design, 69 subjects per treatment group will be required to show superiority (proportion of successes for alicaforsen minus placebo >0) using a two-sided z-test with continuity correction and pooled variance at the 5% significance level and with 95% power.

With 69 subjects per treatment group (138 in total), the study will therefore be powered to show superiority both in terms of the difference of proportions and the odds ratio (both calculations derived using PASS 13 Power Analysis and Sample Size Software (2014). NCSS, LLC. Kaysville, Utah, USA, [ncss.com/software/pass](http://ncss.com/software/pass)).

To demonstrate the superiority of alicaforsen over placebo, both co-primary endpoints must be significant using a two sided CMH test at the 5% significance level. Therefore, a total sample size of 138 subjects will give an overall power of 90% ( $0.95 * 0.95$ ) assuming independence of the two co-primary endpoints.

The randomization is stratified by region (North America vs Rest of World).

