### **1.1.3 Randomisation and Stratification**

The center will dispense the study medication under blinded conditions according to a centrally administered, permuted block randomisation sequence (1:1 ratio for the treatment arms), managed at the study level and implemented using IWRS.

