### **1.1.4 Subject Population/Sets to Be Evaluated**

It is expected that there will be an average of 3 to 4 subjects recruited per site, and hence stratification by study site could be potentially unblinding with respect to the block size given the expected difference in response rates between the two study arms. In accordance with recommendations included in ICH E9 guidelines, the randomisation will therefore be stratified by region, i.e. North America (US and Canada) and Rest of World (Europe, including Israel).

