#### **Full Analysis Set**

The full analysis set (FAS) will consist of all randomized subjects with confirmed active pouchitis at baseline, and who took at least one dose of study drug and have at least one post-

baseline assessment of efficacy. The FAS will be the primary analysis set for analyses of efficacy.

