#### **1.3.2.1 Co-Primary Efficacy Analysis**

The co-primary measures of efficacy will be:

- The proportion of subjects who are in endoscopic remission (Endoscopic Score  $\leq 1$ ), and
- The proportion of subjects who achieve a Stool Frequency Score  $\leq 1$ , at Week 10.

The proportion of subjects who achieve each of the co-primary measures of efficacy at Week 10 will be presented and compared between treatment groups using a Cochran-Mantel-Haenszel test accounting for region. The difference in proportions between the two groups and associated 95% confidence interval will also be presented.

Subjects with a missing endoscopic assessment at week 10, or insufficient stool frequency data, will be declared not to have achieved the respective outcomes.

Secondary analyses of the co-primary endpoints will include investigations of the effect of treatment and baseline characteristics (region, treatment, sex, age group, PDAI score) on the co-primary endpoints using logistic regression models.

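### Minor: the co-primary difference in proportions and its 95% interval are not stratified by region, although randomisation and the deciding CMH test are

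*SAP*

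**What the plan says.** **Design.** Section 1.1.3 describes a "permuted block randomisation sequence (1:1 ratio for the treatment arms"), and section 1.1.4 adds that "the randomisation will therefore be stratified by region", with two strata: North America and Rest of World.

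**Test.** Section 1.2 states: "The primary analysis will be based on a Cochran-Mantel-Haenszel Test (CMH) stratifying by region". It also sets the success rule: "both co-primary endpoints must be significant using a two sided CMH test at the 5% significance level". Section 1.3.2.1 again has the CMH test account for region.

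**Estimate.** Section 1.2 says that the difference in success proportions "and the associated estimated 95% confidence interval) will be presented based on the Z-test". Section 1.3.2.1 says only: "The difference in proportions between the two groups and associated 95% confidence interval will also be presented". Neither place names strata, weights or a variance form for the interval.

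**Elsewhere.** The logistic models in section 1.3.2.1 include region, but a logistic model yields odds ratios, not a difference in proportions. Under Stool Frequency in section 1.3.2.2, the proportion with a score of 0 follows the co-primary method, so it inherits the same estimate.

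**The concern.** The difference and its interval are the plan's only absolute measure of effect for the two co-primary endpoints. A Z-test for two proportions, as named, has no strata. The test therefore respects the design factor and the estimate printed beside it does not.

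Two consequences follow.

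- Stratified allocation removes most between-region variation from the comparison, but the crude variance formula still counts it. If regions differ in prognosis, the interval is wider than it needs to be.
- Estimate and test use different variances, so the interval can include zero although the CMH test is significant.

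What is at stake is the precision and coherence of a reported estimate, not the trial's conclusion.

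**Working it through.** **Inputs from the SAP (section 1.2):** 50% v 20% success; 69 per group; 63 per group for CMH alone; two-sided 5%; 95% power. **Assumed, because the SAP gives none:** the regional split, the regional success rates, the same treatment difference in both regions, and a CMH test without continuity correction.

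**1. The plan's own figures.** Without correction, n = [1.960·√(2·0.35·0.65) + 1.645·√(0.25 + 0.16)]² / 0.30² = (1.322 + 1.053)² / 0.09 = 62.7, so 63, as stated. With continuity correction, n = (62.7/4)·[1 + √(1 + 4/(62.7·0.30))]² = 69.2. Rounding up gives 70 against the stated 69, where power is 94.9%; the difference is immaterial. Neither calculation uses region, so stratifying the interval leaves the sample size alone.

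**2. Half-width by formula.** Crude: 1.96·√[(0.25 + 0.16)/69] = 15.1 points. Now take two equal regions whose rates differ by g in both arms. The average within-region variance per arm is p(1−p) − g²/4, so the stratified half-width is 1.96·√[(0.41 − g²/2)/69]:

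- g = 0: √(0.410/69), 15.1 points
- g = 0.10: √(0.405/69), 15.0 points
- g = 0.20: √(0.390/69), 14.7 points
- g = 0.30: √(0.365/69), 14.3 points

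With a 30:70 regional split the last two become 14.8 and 14.4. In sample-size terms a 20-point gap is worth 0.410/0.390 − 1 = 5%, and a 10-point gap 0.410/0.405 − 1 = 1%.

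**3. Simulation.** 400,000 trials per scenario, with 69 per arm and regions of 35 and 34 per arm. The crude interval is unpooled; the stratified one is Mantel-Haenszel with Sato variance. Half-widths and coverage are at 50% v 20%. The last two columns give the share of trials in which the crude interval includes zero although CMH is significant.

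| Regional gap (points) | Half-width, crude | Half-width, stratified | Coverage, crude | Zero included, 50% v 20% | Zero included, 36% v 20% |
|---|---|---|---|---|---|
| 0 | 15.0 | 15.0 | 94.6% | 0.0% | 0.0% |
| 10 | 15.0 | 14.9 | 94.7% | 0.0% | 0.1% |
| 20 | 15.0 | 14.6 | 95.2% | 0.1% | 0.7% |
| 30 | 15.0 | about 14.2 | 95.9% | 0.4% | 3.2% |

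Stratified coverage stays near 94.6% throughout, and the stratified interval almost never includes zero beside a significant CMH result.

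**4. Agreement with CMH in both directions.** Each interval can also exclude zero when CMH is not significant. Counting both directions:

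- 20-point gap, 40% v 20%: about 0.7% of trials crude, about 1.1% stratified
- 20-point gap, 36% v 20%: about 1.0% crude, about 1.5% stratified
- 30-point gap, 36% v 20%: about 3.2% crude, about 1.5% stratified

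Stratifying removes one kind of conflict but does not improve total agreement everywhere.

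**5. The point estimate.** With equal arms within each region, the crude and Mantel-Haenszel differences coincide. The Full Analysis Set is limited to "all randomized subjects with confirmed active pouchitis at baseline, and who took at least one dose of study drug" and with a post-baseline efficacy assessment, so some imbalance can arise. With 5-10% of subjects excluded at random and gaps of 0 to 20 points, the two estimates differ by 0.1 to 0.5 points on average in absolute terms, with a mean signed difference of zero.

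**The case against.** The strongest reply is that nothing here is invalid. The CMH test alone decides, and the difference is presented in addition to it. A crude difference is a legitimate, readable estimate, unbiased under 1:1 allocation within region, and its interval holds close to 95% coverage in every scenario. A visible loss needs a regional gap of 20 points or more. The SAP gives no sign of one: section 1.1.4 chooses region because stratifying by site could be unblinding, not because region is prognostic. Section 1 also defers detail to a fuller SAP before database lock.

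Most of this stands, and it is why the point is minor. It does not remove the point. The SAP does not leave the method open; it names one that ignores the factor used in both the randomisation and the test. Adjusting for that factor costs nothing if regions are alike and gains a little if they are not.

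Three stronger readings are tempting, and the document supports none of them.

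- A reader might infer that the interval will use the "two-sided z-test with continuity correction and pooled variance at the 5% significance level" form, which would make it clearly too wide. Section 1.2 attaches that form to the sample size calculation only, so no harm is counted for it.
- A reader might infer that the Z-test is a second criterion for success, because section 1.2 describes power for the difference as well as for the odds ratio. The stated success rule names the CMH test alone.
- A reader might infer that a stratified interval will always agree with the CMH test. Step 4 of the working shows that it will not.

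**Conclusion.** The point holds as a minor, nearly free improvement. The co-primary difference and its interval are planned without region, while the design and the deciding test use it, and no other section supplies a region-adjusted difference.

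The gain in half-width at the design assumptions runs from nothing to about 0.8 points (15.0 v about 14.2), depending on a regional gap of 0 to 30 points. The chance of an interval that includes zero beside a significant CMH result is at most 0.4% at 50% v 20%, and about 3% only where a borderline effect (36% v 20%) meets a 30-point gap. These sizes rest on assumed regional rates, a near-equal regional split and a common treatment difference across regions. They do not bear on whether the trial succeeds.

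**What to change.** In section 1.2, replace the reference to the Z-test as the basis of the reported difference and interval with: *as the region-stratified Mantel-Haenszel weighted difference (alicaforsen minus placebo) with a two-sided 95% confidence interval using the Sato variance, without continuity correction*.

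In section 1.3.2.1, where the interval is mentioned without a method, add after it: *stratified by region as in section 1.2*. The Stool Frequency Score of 0 in section 1.3.2.2 then follows through its existing reference to the co-primary method.

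Make the change no later than the SAP finalisation at the blinded data review (section 1.4). It costs two short edits and a standard software option. The CMH test, the success rule, the sample size, the power statement and the data collected stay as they are.

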### **1.1.2 Hypothesis Testing and Confidence Intervals**

All significance probabilities will be two tailed. Statistical tests will be at a 5% level of significance.

Confidence intervals will be 95% two-sided.

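### The 90% overall power at 138 subjects is about 3 points too low for the deciding CMH tests: 0.95 per endpoint is the CMH power at 63 per group, not at 69

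*SAP*

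**What the plan says.** All of the sample size reasoning is in SAP section 1.2.

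- **Assumed rates, both endpoints:** "50% of patients on alicaforsen and 20% on placebo will have a successful treatment outcome".
- **CMH test:** "63 subjects per treatment group will be required to show superiority", for a "two-sided CMH Test at the 5% significance level and with 95% power".
- **z-test:** with continuity correction and pooled variance, 69 per group are needed for the same 95% power. The section adopts 69 per group (138 in total) so that both the odds ratio and the difference in proportions are powered.
- **Success rule:** "both co-primary endpoints must be significant using a two sided CMH test at the 5% significance level".
- **Overall power:** the next sentence concludes that "a total sample size of 138 subjects will give an overall power of 90" per cent, shown as 0.95 × 0.95, with the two endpoints taken as independent.

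Section 1.3.2.1 confirms that the treatment groups are compared on each co-primary endpoint with the CMH test accounting for region. The difference in proportions and its confidence interval are presented alongside it.

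**The concern.** The overall power is drawn as a consequence of the CMH success rule, so it should be the CMH power at 69 per group, squared. The factor used is 0.95, which the same section gives as the CMH power at 63 per group. One test under one set of assumptions cannot need 63 per group for 95% power and still have only 95% at 69. At 69 per group, 0.95 fits the other test in the section, the continuity-corrected z-test.

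What is at stake is the accuracy of the main design figure, since overall power is what a reader takes away from this section. Here it is attached to the wrong test. No decision about enrolment depends on it.

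**Working it through.** **Inputs (SAP sections 1.1.2 and 1.2).** Two-sided α = 0.05, so z = 1.960; p₁ = 0.50, p₂ = 0.20, difference 0.30; 1:1 allocation; pooled rate (0.50 + 0.20)/2 = 0.35; target power 95% per endpoint, so z = 1.645.

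Two terms recur:
- null term: 1.960 × √(2 × 0.35 × 0.65) = 1.960 × 0.6745 = 1.322
- alternative SD: √(0.50 × 0.50 + 0.20 × 0.80) = √0.41 = 0.6403

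**Step 1. Reproduce the SAP's figures.**
- CMH, no continuity correction: n = (1.322 + 1.645 × 0.6403)² / 0.30² = (2.375)² / 0.09 = 62.7, so 63 per group. This matches.
- z-test with continuity correction: the usual correction formula gives 70 against the stated 69. Exact binomial enumeration at 69 gives 95.1%, so 69 is acceptable.
- Overall: 0.95 × 0.95 = 0.9025, the stated 90%.

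**Step 2. Power of each test.** Without correction, power = Φ[(0.30 × √n − 1.322) / 0.6403]. With correction, 0.30 is replaced by 0.30 − 1/n.
- CMH, n = 63: Φ(1.654) = 0.951
- CMH, n = 69: Φ[(2.492 − 1.322) / 0.6403] = Φ(1.827) = 0.966
- Corrected z-test, n = 69: Φ[(2.372 − 1.322) / 0.6403] = Φ(1.639) = 0.949

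| Test | Per group | Per endpoint | Both endpoints, independent |
|---|---|---|---|
| CMH | 63 | 95.1% | 90.4% |
| CMH | 69 | 96.6% | 93.3% |
| z-test, continuity-corrected | 69 | 94.9% (exact 95.1%) | about 90% |

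**Step 3. Check that 96.6% does not depend on the approximation.** Exact enumeration of the uncorrected pooled test at 69 per group gives 0.9660. The normal approximation with the Mantel-Haenszel variance gives 0.965 to 0.966. A simulation of the two-stratum CMH test (400,000 runs) gives 0.966 to 0.967. The simulation assumed the same rates in both regions and region splits of 34/35 and 23/46 per group; the SAP does not state the split.

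**Step 4. Check the independence assumption.** Whatever the dependence between endpoints, joint power is at least 2 × 0.966 − 1 = 93.2% and at most 96.6%. The 90% figure is therefore too low for the CMH rule under any correlation.

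**The case against.** **The 0.95 may be a nominal floor.** The SAP sets 95% as the target for both tests, and at 69 per group both meet it, at least to rounding. On that reading 0.95 × 0.95 is a lower bound that lacks the words *at least*. This is fair, and it is why the point is small. But the sentence as written says what 138 subjects will give under the CMH rule, and that value is not 90%.

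**The CMH test may have been meant with a continuity correction.** At 69 per group that version would have about 94.9% per endpoint and 90% overall, as stated. The SAP mentions no such correction, however, and its figure of 63 per group reproduces only without one: with it, power at 63 falls to about 92.7% and 70 would be needed. Either way, the 63 and the 90% cannot both describe the same test.

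**Stronger readings that the document does not support:**
- *The trial is underpowered.* The reverse is true: under the stated assumptions the deciding rule has more power than claimed.
- *The plan conceals 12 surplus subjects (138 − 126).* Both 63 and 69 are stated openly, and 69 is chosen so that the z-test is powered as well. The extra 6 per group are not surplus to that aim. Nor is 90% a target; it is derived from 95% per endpoint.
- *The extra subjects are the only protection against dropout, and 126 subjects in the Full Analysis Set would secure 90%.* Under section 1.3.2.1, missing Week 10 endoscopy or insufficient stool data count as failure. A subject in the Full Analysis Set (section 1.1.4) who lacks Week 10 data therefore stays in it and lowers the rates, not the sample size. As an illustration, suppose that 50% and 20% apply to completers only and that 6 of 69 per group lack Week 10 data. The rates become 0.50 × 63/69 = 45.7% and 0.20 × 63/69 = 18.3%. Power is then about 94% per endpoint and 88.5% overall, with all 138 still in the set. The SAP does not say whether its rates already include such failures.

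**Conclusion.** The point holds as a misstated power. For the rule that decides the trial, 138 subjects give about 96.6% per endpoint and about 93% overall, against the stated 95% and 90%. The gap is 96.6 − 95 = 1.6 points per endpoint and about 3 points overall, in the conservative direction.

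The result rests on the SAP's rates of 50% and 20% for both endpoints, a CMH test without continuity correction (the only version that reproduces 63 per group), 69 analysed per group, and independence for the 93% figure. It also takes the assumed rates to be those seen after missing Week 10 outcomes are counted as failures. The choice of 138 subjects is not called into question.

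**What to change.** Replace the overall power sentence in SAP section 1.2 with, for example:

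*With 138 subjects the CMH test has about 96.6% power per endpoint and about 93% overall, assuming independence and that the 50% and 20% rates already count missing Week 10 outcomes as failures; the continuity-corrected z-test has about 95% per endpoint and about 90% overall.*

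If the sponsor prefers to keep the present figure, writing *at least 90%* for the CMH rule would be the minimum correction, with the same two assumptions stated. If a continuity-corrected CMH test was intended, the section should say so and revise the 63 per group instead.

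The cost is one sentence. Enrolment, the tests and the success rule stay as they are.

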## **1.3 STATISTICAL ANALYSES**

### **1.3.1 Demographic and Baseline Characteristics**

Subject demographic and baseline characteristic data will be summarised using the standard summary statistics.

### **1.3.2 Efficacy Analysis**

All efficacy analyses and summaries will be performed using the FAS. A confirmatory analysis of the primary efficacy parameter will be carried out using the PPS.

All statistical tests comparing the treatment groups will be two-tailed and at the 5% level of significance.

#### **1.3.2.1 Co-Primary Efficacy Analysis**

The co-primary measures of efficacy will be:

- The proportion of subjects who are in endoscopic remission (Endoscopic Score  $\leq 1$ ), and
- The proportion of subjects who achieve a Stool Frequency Score  $\leq 1$ , at Week 10.

The proportion of subjects who achieve each of the co-primary measures of efficacy at Week 10 will be presented and compared between treatment groups using a Cochran-Mantel-Haenszel test accounting for region. The difference in proportions between the two groups and associated 95% confidence interval will also be presented.

Subjects with a missing endoscopic assessment at week 10, or insufficient stool frequency data, will be declared not to have achieved the respective outcomes.

Secondary analyses of the co-primary endpoints will include investigations of the effect of treatment and baseline characteristics (region, treatment, sex, age group, PDAI score) on the co-primary endpoints using logistic regression models.

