### **Pouchitis intervention**

The proportion of subjects, by week 26, who have not received any additional pouchitis treatment will be calculated and compared between the two treatment groups.

The time to first intervention (including POUCHITIS related surgery) will be calculated for each subject. The time will be calculated in days from the start of study treatment.

Subjects not requiring a rescue intervention during their treatment period will be censored at the time of stopping study treatment in the analysis. Kaplan-Meier curves will be presented and estimates of the probability of no “rescue” intervention at Weeks 3, 6 and 10 will be provided together with their 95% confidence intervals.

In addition, time to first “rescue intervention” will be analyzed using a Cox’s proportional hazards regression model including terms for region, treatment, sex, age group, and the baseline PDAI score.

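### The co-primary non-responder rule covers only missing data, so a subject given additional pouchitis treatment before Week 10 can be scored as a study-drug success

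*SAP*

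**What the plan says.** Section 1.3.2.1 defines the co-primary outcomes at Week 10 as an Endoscopic Score of at most 1 and a Stool Frequency Score of at most 1, each "compared between treatment groups using a Cochran-Mantel-Haenszel test accounting for region". Its only further scoring rule is: "Subjects with a missing endoscopic assessment at week 10, or insufficient stool frequency data, will be declared not to have achieved the respective outcomes".

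Additional treatment appears elsewhere, in the Pouchitis intervention part of section 1.3.2.2, as an efficacy outcome of its own. The proportion of subjects by Week 26 "who have not received any additional pouchitis treatment will be calculated and compared between the two treatment groups". Time to first intervention is also analysed, and the probability of no rescue "intervention at Weeks 3, 6 and 10 will be provided together with their 95% confidence intervals".

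The Full Analysis Set in section 1.1.4 is the primary efficacy set and does not exclude or reclassify subjects who receive additional treatment. The Per Protocol Set might drop some of them, but it is supportive and its exclusion reasons are deferred. Section 1.2 assumes for both endpoints that "50% of patients on alicaforsen and 20% on placebo will have a successful treatment outcome" and does not say how rescued subjects enter those rates.

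**The concern.** The SAP treats additional treatment as an unfavourable outcome in one section and ignores it in the section that decides the trial. A subject can be an event in the time-to-intervention analysis and a success on both co-primary endpoints, and nothing in the document reconciles the two.

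If the comparison is meant to show what alicaforsen does, a response obtained with other treatment should not be credited to the randomised arm. Both co-primary endpoints must be significant, so a distortion affects both tests. The SAP has already chosen to score missing data as failure, so the co-primary section is the natural place for a rule on rescue. Leaving it open also means that it may be settled at the Blinded Data Review Meeting (section 1.4), after the pooled endoscopic remission rate has been seen.

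**Working it through.** **1. Inputs from the SAP.** Success 50% on alicaforsen and 20% on placebo; two-sided 5%; 95% power per endpoint; 63 per group "using a two-sided CMH Test at the 5% significance level and with 95% power"; 69 per group "using a two-sided z-test with continuity correction and pooled variance at the 5% significance level and with 95% power"; 138 in total (section 1.2).

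**2. Reproducing the plan's figures.** With p1 = 0.50, p2 = 0.20 and mean 0.35,

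n = [1.960·√(2·0.35·0.65) + 1.645·√(0.50·0.50 + 0.20·0.80)]² / 0.30² = (1.322 + 1.053)² / 0.09 = 62.7, so 63 per group. This matches the stated CMH figure (treated here as one stratum).

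With continuity correction, (62.69/4)·[1 + √(1 + 4/(62.69·0.30))]² = 69.2. That rounds up to 70 against the stated 69, but exact binomial enumeration of the corrected test at 69 per group gives 95.1% power, so 69 is sound. Overall, 0.95 × 0.95 = 0.9025. The sample size is not in dispute.

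**3. Model for rescue.** Assumptions, none of them given in the SAP:
- 50% and 20% are the rates with rescued subjects counted as failures.
- Rescued subjects come from those failures and have Week 10 data.
- R is the share of the whole arm rescued before Week 10, and s = 0.5 is the share of those scored as successes.

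The scored rate is then 0.50 + 0.5·R(active) on alicaforsen and 0.20 + 0.5·R(placebo) on placebo. For 20% on placebo and 10% on active: 0.50 + 0.05 = 0.55 and 0.20 + 0.10 = 0.30.

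**4. Power at 69 per arm.** Exact binomial enumeration of the single-stratum CMH test. The last column squares the per-endpoint power, using the SAP's own independence assumption.

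| Rescued, placebo / active | Scored rates, active vs placebo | Difference | Power per endpoint | Both endpoints |
|---|---|---|---|---|
| none credited | 50% vs 20% | 30 points | 96.6% | 93% |
| 10% / 10% | 55% vs 25% | 30 points | 95.4% | 91% |
| 20% / 20% | 60% vs 30% | 30 points | 94.9% | 90% |
| 20% / 10% | 55% vs 30% | 25 points | 84.8% | 72% |
| 30% / 10% | 55% vs 35% | 20 points | 65.8% | 43% |
| 10% / 20% | 60% vs 25% | 35 points | 98.9% | 98% |

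The last row shows the reversal: more rescue on active widens the difference to 35 points.

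**5. The other denominator.** If r is instead the share of *non-responders* rescued, the arms gain 0.5·r·s (active) and 0.8·r·s (placebo), because 50% and 80% of subjects are non-responders. Equal r then shrinks the difference to 30·(1 − r·s) points. At r = 20% and s = 50% this is 55% vs 28%, or 27 points, with power 90.5% (normal approximation). With equal s, the difference shrinks only if 0.8·r(placebo) > 0.5·r(active). It widens if active non-responders are rescued more than 0.8/0.5 = 1.6 times as often as placebo non-responders.

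**6. Lower rescue success.** With 20% and 10% rescued and s = 30%, the rates are 53% vs 26% and power is 90.5%. With s = 20%, they are 52% vs 24% and power is 92.9%.

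**The case against.** **The protocol is not shown.** It may withdraw rescued subjects or end their assessments. They would then have no Week 10 data, the missing-data rule would already make them failures, and the effect would be nil. This stands as a limit on the size. It does not remove the gap, because the SAP states no such rule and scoring is a matter for the analysis plan.

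**Scoring observed outcomes is a legitimate choice.** A treatment-policy analysis uses the Week 10 result whatever else was given, while counting rescue as failure is a composite strategy. This also stands. The fault is that the plan does not state its choice, although it scores rescue as unfavourable elsewhere. The bias described here is bias relative to the effect of the study drug itself.

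**The document describes itself as preliminary.** It says that a detailed SAP will follow. That lessens the weight of the omission, but this text already writes the failure rule and leaves out an event that it analyses elsewhere.

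**Evidence of frequency is thin.** Weeks 3, 6 and 10 are also the estimate times for clinical remission, so they show that rescue is measured and thought possible by Week 10, not that it is common.

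A reader might infer that the omission necessarily dilutes the treatment effect. The documents do not support that. They give no rescue rate by arm, equal rescue as a share of each arm leaves the 30-point difference intact, and the direction reverses if rescue is sufficiently commoner on active.

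**Conclusion.** The gap is real. Followed as written, the co-primary analysis can count a subject given additional pouchitis treatment before Week 10 as a success. The plan should settle this before unblinding.

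The size is uncertain. Under the stated assumptions, equal rescue of 10% or 20% of each arm costs less than two percentage points of power per endpoint (95.4% or 94.9% against 96.6%). Rescue of 20% on placebo and 10% on active brings power to 84.8%, and 30% and 10% to 65.8%. Dilution is a reasonable expectation if the drug works and non-responders are the ones rescued, but it is not established.

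Nor do these figures show that the trial is underpowered. The statement "With 69 subjects per treatment group (138 in total), the study will therefore be powered to show superiority" reproduces on its own assumptions. If the 50% and 20% were meant as rates observed regardless of rescue, no planned power is lost and the issue is only one of interpretation.

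**What to change.** - **Co-primary rule.** Add to section 1.3.2.1 that a subject with an additional pouchitis intervention before the Week 10 assessment is counted as not having achieved either co-primary outcome.
- **One definition.** Define the event once and use it both here and in the time-to-first-intervention analysis. That section now refers to additional treatment, to intervention and to rescue without defining any of them. For the co-primary rule, the window should run to the Week 10 assessment even if study treatment has already stopped, because the time-to-event analysis censors rescue-free subjects when treatment stops.
- **Secondary responder endpoints.** Apply the rule with a visit-specific cut-off: an intervention before that visit's own assessment. A single Week 10 cut-off would wrongly erase Week 6 PDAI and histology responses in subjects treated only after Week 6.
- **Sensitivity analysis.** Report the co-primary comparison on observed outcomes regardless of intervention, keeping the existing missing-data rule.

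The cost is a few sentences and one sensitivity table; the time-to-intervention analysis already needs the dates. Observed success rates may be slightly lower in both arms. The change affects scoring only, not who receives additional treatment or when.
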